4. OBJECTIVES*

Aim 1: Draw upon the literature and a User Centered Design approach to collect data from content area experts, caregivers, and individuals with lived experience of perinatal depression, to iteratively develop the Text4Moms tool (tailored text messages, video content, and peer navigator dashboard).

Aim 2: Evaluate preliminary effect direction and magnitude of Text4Moms in a pilot randomized trial (Text4Moms vs educational texts; ratio 2:1) with 30 at-risk pregnant individuals not in an MDE. *Compared to participants randomized to the control condition, those in Text4Moms will:* **H1:** show target engagement through improvement in “self-efficacy” of $\geq d = 0.2$ that can protect against development of an MDE; **H2:** show greater decline in Edinburgh Postnatal Depression Scale (EPDS) scores of $\geq d = 0.2$, and items indicative of RDOC constructs of “loss” and “threat.”¹

Aim 3: Examine implementation outcomes by evaluating the usage, acceptability, and feasibility of Text4Moms and its components: **H3:** Participant ratings will average at least 68 on the System Usability Scale for the Text4Moms system and components. **H4:** >70% of patients will show engagement in Text4Moms by opening $\geq 80\%$ of text messages and clicking on $\geq 30\%$ of links to enhanced content. **H5:** $\geq 30\%$ of mothers will engage with the chat and endorse 4 out of 5 on its utility.

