The baseline assessment will be short and will not duplicate information from the screening and eligibility assessment. Individuals will receive a brief reassessment at 4 weeks that includes the EPDS, the CAT-MH, the General Self Efficacy Scale (GSE Scale), the System Usability Scale (SUS)¹¹⁴ and User Engagement Scale (UES)¹¹⁵ that will allow us to collect and address areas related to usability and ensure the intervention content is accessible to all participants. There will be an 8 week assessment that repeats these questions and the CAT-MH. The final assessment will also include the SUS and UES as well as questions on satisfaction of the system, relevance to their issues, what they liked about the system, and what they did not like. Study staff will contact all participants at 3 months to obtain additional qualitative input. The research team will also evaluate the number of individuals who ask to stop texts, number of texts received, and number of links that are opened.

INVESTIGATOR STUDY PLAN - REQUIRED

- Select items from the Inventory of Depressive Symptomatology (QIDS)¹²² that map onto RDOC domains⁵¹ of negative valence (loss and threat) and positive valence (hedonia and reward): impaired capacity for pleasure, impaired general interest, impaired mood response to desired events, impaired energy level for reward and feeling anxious or tense, panic/phobia, interpersonal sensitivity for loss and threat. This will illustrate salience with RDOC constructs that map onto neural pathways that are putatively linked with depression.

MEASURE	Baseline	4 Wks	8 Wks
EPDS	X	X	X
MOS	X		X
QIDS items that track RDOC	X		
CAT-MH	X	X	X
General Self Efficacy	X	X	X
System Usability Scale	X	X	X
User Engagement Scale	X	X	X

- The CAT-MH including the CAT-DI¹¹² is a computerized adaptive test that draws from an item bank of 452 items; individuals typically need to answer 12 items to render an accurate diagnosis of an MDE. The CAT-DI module has a sensitivity of 0.92 and specificity of 0.88 when compared to the Structured Clinical Interview for DSM-IV. The CAT-MH is integrated into CIAS 3.0, allowing for seamless integration with other assessments. This will determine who has depression and needs intervention at the outset of the study (exclusion criteria) and will be used as an outcome measure to determine if the intervention decreased the risk of an MDE or anxiety disorder.

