- The General Self Efficacy Scale (GSE scale)⁶⁸ has 10 items scored from 1-4 that measures an individual's belief that she can respond to novel or challenging situations. It takes ~2-4 minutes to complete, has a Chronbach's alpha of 0.82-0.93 and in individuals, is a single factor and correlated highly with self esteem and optimism. This is a target of the intervention that is putatively linked with depression risk. We evaluate whether the TMI changes self-efficacy and hence risk of an MDE.
- The Pearlin Mastery Scale (PMS)¹¹³ has 7 items that are scaled 1-4 (1= strongly disagree to 4= strongly agree) with a range of 7-28, and low scores indicating low mastery (Chronbach's alpha=0.78). This is also a target of the intervention and may be associated with lower risk of worsening depression.
- System Usability Scale¹¹⁴ has 10 items and is scored 1-5 (strongly agree to strongly disagree). Scores are summed and multiplied by 2.5. A score of greater than 68 is considered above average. This is a measure of acceptability that bears on ability to implement the system.
- User Engagement Scale – short form¹¹⁵ is a 12 item scale that scores from strongly disagree to strongly agree (1-5). It has 4 subscales with 3 items each. The subscales are Focused Attention; Perceived Usability; Aesthetic Appeal; Endurability. The overall reliability (ω) was 0.88 in formative work; subscales have reliability that is close to this statistic. This is an additional measure of acceptability and hence ability to implement the TMI.

Study Process: After randomization, participants will be sent texts 3-4 times per week (this may change depending upon input from the PGG). Texts will be short and for the TMI, will include video links that reinforce information relevant to IPT. Texts will also be tailored for stage of pregnancy, history of perinatal depression, and possibly other factors such as age depending upon input from the PGG and the EAB. Texts will continue for 8 weeks unless the participant elects to “STOP” texts. They will include a button that will invite individuals to chat with a peer.

INVESTIGATOR STUDY PLAN - REQUIRED

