12. DATA AND SPECIMEN BANKING*

De-identified data will be stored in the National Library of Medicine (NLM) on clinicaltrials.gov. Results information will be submitted and will not include individual patient data. Following completion of the study, all identifiers will be permanently deleted after the final report to the sponsor has been completed

13. Data Analysis and Management*

INVESTIGATOR STUDY PLAN - REQUIRED

Data will be collected by tablet and email links in REDCap. Our statistician at Yale will manage the data. To evaluate acceptability and use characteristics, we will collect descriptive statistics on satisfaction, helpfulness, and ease of use (SUS and UES) for the Text4Moms system and components (including chat), measured at the intervention (week 8). For engagement, data from the Text4Moms system will be reported showing the percentage of individuals who engage with Text4Moms and read at least 80% of texts and the percentage of individuals who engage with the chat. Qualitative responses from participants will offer further insight into these outcomes.

For efficacy outcomes, total scores on EPDS, GSE and PMS¹¹³ (scales) and the onset of an MDE will be reported using means and standard deviations; frequencies and percentages for the EPDS, GSE and PMS scores will be reported as linear variables. Multiple regression will be used to test for differences in the EPDS, and the GSE and PMS scores between treatment groups at week 8, adjusting for baseline scores. Generalized estimating equations will be used to explore if changes in EPDS, GSE and PMS scores varied over time from baseline to week 4 and week 8. We will also examine whether the percentage of individuals who experience an MDE at week 4 and/or week 8 differed between treatment groups using chi-square tests.

We will test for target engagement by measuring changes in the self-efficacy construct (GSE and PMS) between the 2 groups at 4 and 8 weeks. We will do the same for RDOC constructs measured with IDS-SR items. As an exploratory analysis, we will estimate correlations between EPDS scores and the GSE and PMS scores with treatment. We note power is not sufficient to detect mediating effects.

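### The assessment schedule collects the RDoC items only at baseline and never collects the Pearlin Mastery Scale, so the planned week-4 and week-8 analyses of both cannot be run

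*Combined protocol and SAP*

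**What the plan says.** **Hypotheses (section 4, Aim 2).** H1 says the Text4Moms arm will "show target engagement through improvement in" self-efficacy, with a benchmark of d = 0.2 or more. H2 expects a greater decline in EPDS "and items indicative of RDOC constructs of" loss and threat.

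**Measures (sections 10 and 11).** PMS is described next to the General Self Efficacy Scale (GSE). Of PMS the plan says: "This is also a target of the intervention and may be associated with lower risk of worsening depression". Section 11 also describes selected QIDS items that map onto the RDoC domains.

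**Analyses (section 13).** Regression is to compare "GSE and PMS scores between treatment groups at week 8, adjusting for baseline scores", and EPDS is treated the same way. A GEE model covers EPDS, GSE and PMS over baseline, week 4 and week 8. Target engagement is the between-group comparison of change at 4 and 8 weeks in a self-efficacy construct made up of GSE and PMS. The plan then adds: "We will do the same for RDOC constructs measured with IDS-SR items".

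**Schedule (section 11).** Table 1 has seven rows. The row "QIDS items that track RDOC" has one mark, at baseline. PMS has no row. The text says: "Individuals will receive a brief reassessment at 4 weeks that includes the EPDS, the CAT-MH, the General Self Efficacy Scale (GSE Scale"), followed by the System Usability Scale (SUS) and the User Engagement Scale (UES). The 8-week assessment repeats this set. The 3-month contact is for qualitative input. For the scales given at baseline, the text points to Table 1.

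**The concern.** Sections 4 and 13 promise results on two measures that the schedule in section 11 does not deliver. A change score needs a value after baseline, and the RDoC items have none. A baseline-adjusted regression needs a baseline value and an outcome, and PMS has neither.

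Staff who build the REDCap forms will work from Table 1, because it is the only place that sets measures against visits. If they follow it, the trial ends without the data for part of H2 and for one of the two scales that section 13 uses to define target engagement. Analysis choices can be revised later, but an assessment that was never given at week 4 or week 8 cannot be recovered.

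**Working it through.** No figure in the plan bears on this point, so the check sets each analysis in section 13 against the visits at which section 11 collects the measure.

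**Step 1: what section 13 needs**

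| Analysis | Measure | Visits needed |
|---|---|---|
| Week-8 regression adjusted for baseline | EPDS, GSE, PMS | baseline, 8 |
| GEE over time | EPDS, GSE, PMS | baseline, 4, 8 |
| Target engagement (change between groups) | GSE, PMS | baseline, 4, 8 |
| Same comparison for RDoC constructs | QIDS/IDS-SR items | baseline, 4, 8 |
| MDE by group | CAT-MH | 4, 8 |

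**Step 2: what section 11 schedules**

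| Measure | Baseline | Week 4 | Week 8 | Needed but not scheduled |
|---|---|---|---|---|
| EPDS | yes | yes | yes | none |
| GSE | yes | yes | yes | none |
| CAT-MH | yes | yes | yes | none |
| RDoC items | yes | no | no | weeks 4 and 8 (2 of 3) |
| PMS | no | no | no | baseline, weeks 4 and 8 (3 of 3) |

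**Step 3: consequence**

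- *RDoC items:* 0 of 2 post-baseline visits are collected, so no change can be computed in either arm.
- *PMS:* 0 of 3 visits are collected. The regression, the GEE model and the target-engagement comparison cannot be fitted for PMS, and the exploratory correlation of EPDS with PMS is lost as well.

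**Step 4: could this be damage from reading the table out of the PDF?** Unlikely. The MOS row in the same table keeps its empty week-4 cell between two marks, so cell positions survived. Shifted cells would not remove a whole PMS row. The text on the 4-week and 8-week assessments also omits both measures.

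**Step 5: does any other section give a collection time?** Section 10 lists PMS as an outcome measure. Section 14 names the IDS and PMS among the assessments to be monitored. Neither gives a visit.

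**Step 6: instrument name.** Section 11 and Table 1 say QIDS, section 13 says IDS-SR and section 14 says IDS. The form to be built is therefore also unclear.

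**Side check.** The plan's one power figure is 80% for d > 1.1 with 20 against 10 participants and two-sided alpha 0.05. By the normal approximation, power = Φ(1.1/√(1/20 + 1/10) − 1.96) = Φ(2.84 − 1.96) = 81.1%. With the noncentral t on 28 degrees of freedom it is 78.3%. The figure reproduces, and this point does not alter it.

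**The case against.** The best reply is that Table 1 is simply incomplete. Sections 10, 11, 13 and 14 all treat PMS as a measure in use, so an oversight in the table is more likely than a decision not to collect it. The text lists are not exhaustive either: Table 1 marks MOS at 8 weeks, and the text does not mention it. Table 1 itself looks loose, since it marks the usability and engagement scales at baseline, before any text has been sent. All of this is fair, and it suggests that the sponsor intends to collect PMS. But no section gives a collection time, and Table 1 remains the only visit-by-measure schedule. Evidence that the sponsor wants the data makes the contradiction more worth correcting.

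A second reply is that H1 as worded names only self-efficacy, and GSE, the scale for it, is collected at all three visits. This stands in part: H1 can still be tested on GSE. What is lost is the PMS component that section 13 writes into the same construct. Likewise, the EPDS part of H2 is intact.

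A third reply is that baseline-only RDoC items may be intended, since section 11 gives them an illustrative purpose. If so, H2 and section 13 are what must change. That is a valid way to reconcile the documents, but it does not show them to be consistent now.

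Finally, this is a 30-person pilot with little power. Aim 2 is there to estimate the direction and size of effects, and limited power is no reason to have no data on a stated outcome.

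**Conclusion.** The point holds. Followed as written, the schedule gives the RDoC items at 1 of 3 needed visits (none after baseline) and PMS at 0 of 3. The RDoC part of H2 and the PMS part of the H1 target-engagement test cannot be analysed. EPDS, GSE and CAT-MH are fully scheduled, so the rest of H1 and H2 and the MDE comparison are unaffected.

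This rests on reading Table 1 as the operative schedule and on its marks having been carried over correctly from the PDF. The text of section 11 supports both. The correction should be made before data collection, because the loss would be permanent.

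**What to change.** Amend Table 1 and the descriptions of the visits in section 11:

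1. Add a PMS row at baseline, 4 weeks and 8 weeks.
2. Add the RDoC items at 4 and 8 weeks.
3. Use one instrument name, QIDS or IDS-SR, in Table 1 and in sections 11, 13 and 14, and list the items that will be scored.

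If the sponsor does not want either measure after baseline, the alternative is to delete the matching analyses from section 13 and the matching parts of H1 and H2, so that the hypotheses promise only what is collected.

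The cost is one protocol edit and a change to the REDCap build. PMS has 7 items, and section 11 lists about 7 RDoC items. The added load per participant is 7 items at baseline, 7 + 7 = 14 at week 4 and 14 at week 8, or 35 item responses in all. That is a few minutes per visit.

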Control Condition: The control condition will be limited to texts related to pregnancy, nutrition and sleep and will avoid elements that have behavioral therapeutic effects. We will develop a set of texts from openly available information about healthy pregnancy. Although this condition is meant to constitute time and attention control as recommended by an NIH expert panel¹²³, we will include material on recognizing depression and links to ways to attain depression treatment and suicide hotline information.

Peers: We will employ 2-3 individuals as peers; these will be individuals who experienced perinatal depression or were close to someone with perinatal depression. We will recruit from social media, contact providers and the local chapters of PSI. Peers will be encouraged to cluster their texts and will be paid hourly for training and meetings and a modest amount for each text (~\$5). CIAS 3.0 will include a variety of phrases, messages and resources that can be copied and pasted into the chat and thus help peers with messaging about content. Chats will be monitored by the study team. This will ensure the safety of participants and peers and will allow the study team to know if the content is being utilized. Peers will have a safety protocol should a participant experience psychiatric worsening and/or develop suicidal ideation.

Randomization. The 30 participants for the pilot will be randomized in a 2:1 ratio for Text4Moms: Educational control. We acknowledge that the short duration of an R34, and the need to spend at least a year building the system, limits our follow-up period. To collect information about the TMI functionality at various times in pregnancy and after delivery, we will stratify enrollment to 15 individuals who are before 24 completed weeks of pregnancy and 15 who are after 24 completed weeks of pregnancy. This will allow us to pilot the TMI in all phases of pregnancy and the postpartum period since the TMI will endure for 8 weeks. The statistician will generate an allocation sequence for a random-permuted block randomization using identification numbers. After a participant meets criteria and provides consent, the statistician will email the research assistant (RA) the randomization condition. The RA will have no prior knowledge of the randomization sequence. Randomization will occur by the toss of a coin and will not rely on factors other than the stratification.

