16. RISKS TO SUBJECTS*

The potential risks in this study are loss of confidentiality for participants. Although not due to the study, we may also identify individuals in an MDE or who have suicidal thoughts.

Loss of Confidentiality:

A research assistant, Project Director, or Investigator will obtain verbal and written/virtual consent to screen and then enroll. Information will all be coded under a subject ID and kept on password protected data bases and in double locked files in the offices of research staff.

In addition to being made aware of possible risks via the consent process, participants will be protected against potential risks in several further ways.

1. The use of technology for gathering self-report data enhances participant protection, in that participant data or group assignment will not be available to anyone in the participant's clinic or hospital setting. Even the research assistant is unable to access participant responses.
2. The web-based CIAS software in this study uses 256-bit AES encryption in order to protect data in transit from the participant's electronic device to the dedicated and secured server on which the software resides. CIAS resides on a HIPAA-compliant MSU server with data encryption at rest, dual-factor authentication, malware protection, 24 x 7 monitoring of event notification, and a dedicated and fully managed firewall with active intrusion detection and prevention and access tracking.
3. Possible distress will be noted clearly in the informed consent information sheet, which will also indicate that a referral for counseling is available from the RA. In addition, in order to prevent risk regarding guilt, all intervention content is phrased as positively as possible. We will have staff available during the day should someone require immediate evaluation for depression or suicidal ideation.
4. The informed consent information sheets will explicitly acknowledge the limited security of text messages, both because they are not encrypted, and because the participant's phone itself may be accessible to others. Further, text messages—although tailored—will be written in a way that does not imply any details of the participant's mood; that is, they will look like general advice that might be provided to any pregnant individuals. Finally, participants will be informed that they can end the text messaging plan at any time by texting back "STOP."

Depression Risk and Management of Suicidal Patients:

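### Only a participant's STOP ends texts before 8 weeks, and no listed follow-up item asks about the pregnancy, so pregnancy texts can continue after a loss

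*Combined protocol and SAP*

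**What the plan says.** The rule on duration is in section 11, Study Process: "Texts will continue for 8 weeks unless the participant elects to" STOP them. Section 16 repeats this as the participant's own action: "participants will be informed that they can end the text messaging plan at any time by texting back" that word. Section 15, on withdrawal without consent, is marked not applicable.

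On follow-up, section 11 (Assessments) says: "Individuals will receive a brief reassessment at 4 weeks that includes the EPDS, the CAT-MH, the General Self Efficacy Scale", with two usability scales. Week 8 repeats these and adds the social support measure and satisfaction questions. After that, "Study staff will contact all participants at 3 months to obtain additional qualitative input". Nothing listed asks whether the participant is still pregnant or has delivered. An intention to terminate is an exclusion checked at entry.

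On content, section 11 (Control Condition) says of the control texts: "We will develop a set of texts from openly available information about healthy pregnancy". They also cover nutrition, sleep, recognising depression, and treatment and suicide-hotline links. In the intervention description, "Texts will also be tailored for stage of pregnancy, history of perinatal depression" and possibly other factors. How stage is updated after entry is not stated.

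**The concern.** Participants are enrolled because they are at risk of depression, and half of the pilot enters before 24 completed weeks. Healthy-pregnancy advice sent after a miscarriage or stillbirth is foreseeable and avoidable distress.

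STOP is a blunt answer because it ends all texts. Future texts would have carried the peer-chat link, or the micro-interventions that also lead to chat (section 11), and reminders of the warm line and hotline (section 14). For controls they would have carried depression-treatment and suicide-hotline links. A bereaved participant can therefore escape the pregnancy content only by losing the support content too.

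A lesser matter is interpretation. Section 11 (Randomization) gives the reason for the gestational strata: "To collect information about the TMI functionality at various times in pregnancy and after delivery". No listed item records when delivery occurred.

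**Working it through.** The plan gives no figure on pregnancy loss, so there is none to reproduce, and its power statement plays no part here.

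**1. Can any other stated route end the texts?**
- Monitored peer chat (section 11): could reveal a loss, but chat is a Text4Moms component and is not tied to ending texts.
- Weekly adverse-event review and follow-up after worsening (section 14): could reveal a loss; neither is tied to texts.
- Discontinuation by the investigator after an SAE (section 14): could end participation, but it is discretionary and needs the loss to be reported and judged an SAE first.
- Severe-score alerts (section 16), referral at any point (section 17) and clinician sharing of CAT-MH results (section 21): these respond to symptoms, not to pregnancy status.
- Contact with the reproductive health provider or prenatal site (sections 14 and 24): described as the team contacting them. No return report of pregnancy outcome is described.

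Several routes could bring a loss to light. None asks about the pregnancy or says that texts then change.

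**2. How many losses?** Inputs: 15 early entrants (section 11); 2:1 allocation, so about 15 × 1/3 = 5 early controls if the ratio holds within the stratum; risk p over 8 weeks assumed at 1% to 5%, since the documents give no rate.

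| Group | n | Expected = n × p | Chance of at least one = 1 − (1 − p)^n |
|---|---|---|---|
| Early entrants | 15 | 0.15 to 0.75 | 0.14 to 0.54 |
| Early controls | 5 | 0.05 to 0.25 | 0.05 to 0.23 |

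If the same risk is applied to all 10 controls, the expected number is 10 × p = 0.1 to 0.5.

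**3. How many texts?** Input: 3 to 4 a week for 8 weeks, a frequency the plan says may change.
- Full course: 8 × 3 to 8 × 4 = 24 to 32.
- Left after a loss at the end of week 1: 7 × 3 to 7 × 4 = 21 to 28.
- Sent before a week-4 item could act: 3 × 3 to 3 × 4 = 9 to 12.
- Preventable by a week-4 item: 4 × 3 to 4 × 4 = 12 to 16.
- Preventable by a week-8 item: none, because texts have ended.

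These are upper limits for pregnancy content, since control texts cover other topics too. A report made at once, for example by keyword, could prevent all 21 to 28.

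**4. Delivery timing.** Suppose births fall at 37 to 42 weeks. Status at week 8 is then uncertain for entry at 29 to 34 weeks (37 ≤ g + 8 < 42), and status at week 4 for entry at 33 to 38 weeks (37 ≤ g + 4 < 42). With the 3-month contact taken as 13 weeks from entry, the earliest of these have reached 29 + 13 = 42 weeks, so one question there recovers the date.

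**The case against.** The strongest reply is that silence in the assessment list proves little. The list is visibly incomplete: the Pearlin Mastery Scale is analysed at week 8 in section 13 but is missing from the schedule. Consent pages were removed before review, and the peer safety protocol is not reproduced. Content is also still to be designed: Aim 1 asks the patient group what to avoid, asks the expert board about tailoring and deterioration, and runs a field pre-pilot. This stands as a caution. A reader might infer that the team will not ask about the pregnancy or will not learn of a loss, and the documents do not support that. The duration rule, however, is a positive statement, and nothing in the Aim 1 work requires it to change.

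A reader might also infer that both arms are equally exposed, because section 16 says of the texts that "they will look like general advice that might be provided to any pregnant individuals". That sentence is a confidentiality measure, so that texts do not betray mood, and it does not describe their topics. Text4Moms content is based on interpersonal therapy. That arm is not exempt, since its texts follow stage of pregnancy, but the concern lies chiefly with controls.

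Events are few, and a participant can end texts with one word. Both points are true. They limit the weight of the concern but do not answer it, because that word also ends the support links. It is also fair that delivery timing enters no planned analysis.

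**Conclusion.** The concern holds as a low-frequency safety gap. As written, texts stop early only on STOP, no listed follow-up item asks about the pregnancy, and no other safeguard is linked to the texts. Zero or one loss is the likely experience among early entrants, and fewer among early controls; this rests on the assumed 1% to 5% risk. The exposure per event, at most 21 to 28 texts after a loss at the end of week 1, rests on the planned frequency.

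A reader might go further and infer that the trial lacks safety oversight or that the week-8 comparison is biased. The documents support neither: monitoring, alerts and referral are described, and so few events give no basis for claiming a distorted group difference. The delivery-date point is minor and descriptive.

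**What to change.** Amend the duration rule in section 11 along these lines: texts run for 8 weeks unless the participant sends STOP or a pregnancy loss is reported by any route (reply keyword, week-4 item, chat, staff or provider contact). After such a report, pregnancy-related texts stop in either arm, support resources are offered, and the participant may choose to keep non-pregnancy support messages.

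- Explain the keyword at consent. It is the fastest route and does not wait for an assessment.
- Have CIAS apply the rule automatically, including any chat link retained for Text4Moms, so that staff concerned with outcomes need not learn the arm.
- Add one optional item at week 4: still pregnant; delivered, with date; no longer pregnant. Send the last answer to the study team through the alert route in section 16.
- If wanted, repeat the item at week 8 or the 3-month contact, only to record delivery date for describing use before and after birth.
- Keep all randomised participants in the week-8 comparison.

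The cost is a short amendment to section 11, a line at consent, one item at an existing assessment and minor programming. The question is sensitive and, under section 27, may be skipped. The week-4 item finds a week-1 loss three weeks late, which is why the rule must accept reports by any route.
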